6.1. Endpoints

6.1.1. Primary Endpoint:

Impact of the following factors on the number of treatment escalations of Tofacitinib patients in 24 months

- a. DAS28-4 with Erythrocyte Sedimentation Rate (ESR)
- b. Δ DAS28-4 (ESR)
- c. Physician Global Assessment of Arthritis
- d. Patient's Assessment of Arthritis Pain
- e. Patient's satisfaction with drug treatment
- f. Patient's Global Assessment of Arthritis

Treatment escalation in this study is defined as a switch to another DMARD or combination of DMARDs when compared to the last visit.

6.1.2. Secondary Endpoints:

- a) Time to first treatment escalation
- b) Rate of Low Disease Activity (LDA) over time of patients on Tofacitinib (in combination therapy or monotherapy), as assessed by: Simplified Disease Activity Index (SDAI) \leq 11; Clinical Disease Activity Index (CDAI) \leq 10; DAS 28-4 (ESR) \leq 3.2 and DAS28-4 with C-reactive Protein (CRP) \leq 3.2.
- c) Rate of remission over time of patients on Tofacitinib (in combination therapy or monotherapy), as assessed by: American College of Rheumatology (ACR)-EULAR Boolean remission criteria; SDAI \leq 3.3; CDAI \leq 2.8; DAS 28-4 (ESR) $<$ 2.6 and DAS28-4 (CRP) $<$ 2.6
- d) Change from baseline over time of patients on Tofacitinib (in combination therapy or monotherapy) in DAS 28-4 (ESR) and DAS 28-4 (CRP)
- e) Change from baseline of duration of morning stiffness over time of patients on Tofacitinib (in combination therapy or monotherapy)

- f) Change from baseline in the Functional Ability Questionnaire Hannover (FFbH) over time of patients on Tofacitinib (in combination therapy or monotherapy)
- g) Rate of patients with functional remission in FFbH (FFbH > 83%) over time of patients on Tofacitinib (in combination therapy or monotherapy)
- h) Change from baseline in a self-report questionnaire (a quality of life instrument) developed by the European Quality of Life (EuroQoL) Group (EuroQoL EQ-5D) over time of patients on Tofacitinib (in combination therapy or monotherapy)
- i) Change from baseline in Functional Assessment of Chronic Illness Therapy (FACIT)-Fatigue scale over time of patients on Tofacitinib (in combination therapy or monotherapy)
- j) Drug survival at month 12, 24 of patients on Tofacitinib (in combination therapy or monotherapy)
- k) Patient's satisfaction with Tofacitinib treatment (in combination therapy or monotherapy) over time

7. RESEARCH METHODS

7.1. Study design

This is a 60-month, prospective, non-interventional, multi-centre study to evaluate the impact of the following factors on the number of treatment escalations of Tofacitinib patients in 24 months.

[figure not shown]
Eligible patients will be followed up from the date of first Tofacitinib prescription for 24 months. Patients who are switched from the initial Tofacitinib therapy to other therapies will also be followed up to 24 months. Patient documentation is expected quarterly as per standard clinical practice.

This study observes drug prescription and follow-up visits in daily medical care. Therapeutic strategies and frequency of patient follow-up are decided by the treating physician.

7.2. Setting

The planned recruitment period is 36 months. With planned observation duration of 24 months per patient, the entire study would thus last for 60 months. The study is to start in October 2017 and will end in October 2022. Overall, about 1500 patients in about 200 centres in Germany are to be included in this non-interventional study.

Figure 1. Timelines

7.2.1. Inclusion criteria

Patient eligibility should be reviewed and documented by an appropriately qualified member of the healthcare professional's (HCP) study team before patients are included in the study.

Patients must meet all of the following inclusion criteria to be eligible for inclusion in the study:

1. Patients aged \geq 18 years
2. Confirmed Diagnosis of Rheumatoid Arthritis by rheumatologist
3. Patient is eligible for Tofacitinib treatment according to Summary of Product Characteristics (SmPC)
4. Evidence of a personally signed and dated informed consent document indicating that the patient (or a legally acceptable representative) has been informed of all pertinent aspects of the study.

7.2.2. Exclusion criteria

Patients meeting any of the following criteria will not be included in the study:

1. Contraindications according to Xeljanz® SmPC
2. Receipt of any investigational drug within 3 months before study inclusion

3. Patients who have received any previous treatment with Tofacitinib or other JAK inhibitors
4. Patients who are investigational site staff members or patients who are Pfizer employees directly involved in the conduct of the study.

7.3. Variables

Variable	Role	Data source(s)	Operational definition
RA-treatment with Tofacitinib and/or other DMARDs - date of initiation	Exposure, Potential confounder, subgroup identifier	Case records and electronic Case Report Form (eCRF)	Details will be provided in Statistical Analysis Plan
RA treatment with Tofacitinib and/or other DMARDs – dose	Exposure, Potential confounder, subgroup identifier	Case records/eCRF	Details will be provided in Statistical Analysis Plan
RA treatment with Tofacitinib and/or other DMARDs - tolerability	Potential confounder, subgroup identifier	Case record/eCRF	Details will be provided in Statistical Analysis Plan
RA treatment with Tofacitinib and/or other DMARDs – route of administration	Potential confounder, subgroup identifier	Case record/eCRF	Details will be provided in Statistical Analysis Plan
Age	Baseline characteristic, potential confounder, sub-group identifier	Case records/eCRF	Details will be provided in Statistical Analysis Plan
Gender	Baseline characteristic, potential confounder, sub-group identifier	Case records/eCRF	Details will be provided in Statistical Analysis Plan
Height	Baseline characteristic, potential confounder, sub-group identifier	Case records/eCRF	Details will be provided in Statistical Analysis Plan
Weight	Baseline characteristic, potential confounder, sub-group identifier	Case records/eCRF	Details will be provided in Statistical Analysis Plan
Insurance Type	Baseline characteristic, Potential confounder, subgroup identifier	Case records/eCRF	Details will be provided in Statistical Analysis Plan
Date of first Diagnosis of RA	Baseline characteristic, potential confounder, sub-group identifier	Case records/eCRF	Details will be provided in Statistical Analysis Plan

Tofacitinib citrate

A3921302 OBSERVATIONAL PLAN NON-INTERVENTIONAL STUDY

Final, 23 August 2017

Smoking history and current smoking status	Baseline characteristic, potential confounder, sub-group identifier	Case records/eCRF	Details will be provided in Statistical Analysis Plan
Comorbidities	Baseline characteristic, potential confounder, sub-group identifier	Case records/eCRF	Details will be provided in Statistical Analysis Plan
Erythrocyte Sedimentation Rate (ESR) and C-Reactive Protein (CRP)	Baseline characteristics and outcome variable	Case records/eCRF	Details will be provided in Statistical Analysis Plan
Rheumatoid Factor (RF), Anti-citrullinated protein antibodies (ACPA)	Baseline characteristic, potential confounder, sub-group identifier	Case records/eCRF	Details will be provided in Statistical Analysis Plan
Prognosis factors	Baseline characteristic, potential confounder, sub-group identifier	Case records/eCRF	Details will be provided in Statistical Analysis Plan
Prior drug treatment for RA	Potential confounder, sub-group identifier	Case records/eCRF	Details will be provided in Statistical Analysis Plan
Concomitant treatment of RA with Glucocorticoids	Potential confounder, sub-group identifier	Case records/eCRF	Details will be provided in Statistical Analysis Plan
Patient's Global Assessment of Arthritis	Baseline and outcome variable	Case records/eCRF	Details will be provided in Statistical Analysis Plan
Physician's Global Assessment of Arthritis	Baseline and outcome variable	Case records/eCRF	Details will be provided in Statistical Analysis Plan
Patient's Assessment of Arthritis Pain	Baseline and Outcome	Case records/eCRF	Details will be provided in Statistical Analysis Plan
Tender and swollen (28) joint count	Baseline and Outcome	Case records/eCRF	Details will be provided in Statistical Analysis Plan
Duration of Morning Stiffness	Baseline and Outcome	Case records/eCRF	Details will be provided in Statistical Analysis Plan
Functional Ability Questionnaire Hannover (FFbH)	Baseline and Outcome	Case records/eCRF	Details will be provided in Statistical Analysis Plan
EuroQoL EQ-5D-3L Health State Profile	Baseline and Outcome	Case records/eCRF	Details will be provided in Statistical Analysis Plan
Functional Assessment of Chronic Illness Therapy (FACIT) Fatigue Scale	Baseline and Outcome	Case records/eCRF	Details will be provided in Statistical Analysis Plan
Patient's satisfaction with drug treatment	Baseline and Outcome	Case records/eCRF	Details will be provided in Statistical Analysis Plan

Table 6 Variables

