Despite insufficient response after 3 to 6 months therapy, treat-to-target recommendations of EULAR were only applied in 50% of the German course and prognosis of early arthritis cohort (CAPEA).[14] In an analysis of a cohort from the “Kerndokumentation”, a national database of the German Collaborative Arthritis Centres, 45% of patients were not within DAS28 low disease activity range and therefore would have needed adaption of therapy according to current treatment guidelines. In contrast, rheumatologists’ global assessment of disease activity differed, 80% perceived their patients to be in the low disease activity range and, hence, as being adequately treated.[15]

These observations suggest that in a real-world setting, criteria other than calculated DAS28 remission or low disease activity alone may guide treatment decisions. Among such criteria, satisfaction with drug treatment is of particular interest. On the one hand, a patient who is content with his current therapy is less likely to be willing to change a therapy solely to achieve a better DAS28 score. On the other hand, patient preference and satisfaction of a therapy strongly affects adherence to a prescribed medication, ultimately affecting treatment outcome and efficacy. A factor known to impact on patient satisfaction with a prescribed treatment is the route of administration. Here, several studies point to a preference for oral therapies, also among second-line DMARDs.[16,17]

Recently, Tofacitinib, an orally applied DMARD of the new class called Janus-Kinase-Inhibitors (JAK-Inhibitors) has been brought into the market in the European Union. Tofacitinib is indicated in combination with methotrexate (MTX) for the treatment of moderate to severe active rheumatoid arthritis (RA) in adult patients who have responded inadequately to, or who are intolerant to one or more DMARD. Due to oral administration of Tofacitinib, the impact of patient’s satisfaction with drug treatment on therapy decisions by rheumatologists may be especially pronounced.

EULAR recommendations have now endorsed individual patient related factors such as patient preferences and comorbidities as an overarching principle in the management of RA.

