7.5.1.1. Baseline visit

The following parameters will be documented at baseline visit

- Informed Consent.
- Prognostic factors (from prior history)
- Documentation of initial diagnosis of RA
- Documentation of relevant comorbidities
- Demographic data
- Documentation of insurance type
- Physical Examination (weight, height)
- Smoking history and current smoking status
- Inclusion/ Exclusion criteria according to protocol
- Varicella vaccination status
- RA-Treatment with Tofacitinib and/or other DMARDs
- Prior drug treatment of RA
- Concomitant treatment of RA with Glucocorticoids
- Inflammatory Markers:
 - Erythrocyte sedimentation rate (ESR)

- C-reactive protein (CRP)
- Number of swollen and tender joints
- Duration of Morning stiffness
- Patient's Global Assessment of Arthritis
- Physician's Global Assessment of Arthritis
- Patient's Assessment of Arthritis Pain
- Functional Ability Questionnaire Hannover (FFbH)
- EuroQoL EQ-5D-3L Health State Profile
- FACIT – Fatigue Scale
- Patient's overall satisfaction with prior drug treatment

7.5.1.2. Scheduled Visits 2- 8 /month 3 – month 21

Following parameters will be documented at each interim visit:

- RA treatment with Tofacitinib and/or other DMARDs
- Concomitant treatment of RA with Glucocorticoids
- Inflammatory Markers:
 - Erythrocyte sedimentation rate (ESR)
 - C-reactive protein (CRP)
- Documentation of Adverse Events (AE)
- Number of swollen and tender joints
- Duration of Morning stiffness
- Patient's Global Assessment of Arthritis
- Physician's Global Assessment of Arthritis

- Patient's Assessment of Arthritis Pain
- Functional Ability Questionnaire Hannover (FFbH)
- EuroQoL EQ-5D-3L Health State Profile
- FACIT – Fatigue Scale
- Patient's satisfaction with drug treatment

7.5.1.3. Final (or close out) Visit 9 / month 24

Following parameters will be documented at final visit:

- RA treatment with Tofacitinib and/or other DMARDs
- Concomitant treatment of RA with Glucocorticoids
- Inflammatory Markers:
 - Erythrocyte sedimentation rate (ESR)
 - C-reactive protein (CRP)
- Documentation of AE
- Number of swollen and tender joints
- Duration of Morning stiffness
- Patient's Global Assessment of Arthritis
- Physician's Global Assessment of Arthritis
- Patient's Assessment of Arthritis Pain
- Functional Ability Questionnaire Hannover (FFbH)
- EuroQoL EQ-5D-3L Health State Profile
- FACIT – Fatigue Scale
- Patient's satisfaction with drug treatment

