7.5.2. Schedule of Activities

The schedule of activities table provides an overview of the visits that may be documented. Refer to the STUDY PROCEDURES and ASSESSMENTS sections of the protocol for detailed information on each documentation and assessment.

According to his clinical practice the HCP may schedule visits (unplanned visits) in addition to those listed on the schedule of activities, in order to conduct evaluations or assessments required to protect the well-being of the patient. As this is a non-interventional study none of these visits are mandatory and every visit should be scheduled according to clinical practice.

Table 7. Schedule of Activities

Study Week	Baseline (Enrolment)	Month 3	Month 6	Month 9	Month 12	Month 15	Month 18	Month 21	Month 24
Visit Number	1	2	3	4	5	6	7	8	9
Informed Consent	x								
Initial diagnosis of RA	x								
Prognostic factors	x								
Relevant comorbidities	x								
Demographic data	x								
Insurance type	x								
Smoking history and current smoking status	x								
Physical Examination (weight, height)	x								
Inclusion/Exclusion criteria	x								
Varicella vaccination status	x								
Prior drug treatment of RA	x								
RA-treatment with Tofacitinib and/or other DMARDs	x	x	x	x	x	x	x	x	x
Concomitant treatment of RA with Glucocorticoids	x	x	x	x	x	x	x	x	x

Tofacitinib citrate

A3921302 OBSERVATIONAL PLAN NON-INTERVENTIONAL STUDY

Final, 23 August 2017

Inflammatory Markers	x	x	x	x	x	x	x	x	x
Documentation of AE	x	x	x	x	x	x	x	x	x
Number of swollen and tender joints	x	x	x	x	x	x	x	x	x
Duration of Morning stiffness	x	x	x	x	x	x	x	x	x
Patient's Global Assessment of Arthritis	x	x	x	x	x	x	x	x	x
Physician's Global Assessment of Arthritis	x	x	x	x	x	x	x	x	x
Patient's Assessment of Arthritis Pain	x	x	x	x	x	x	x	x	x
Functional Ability Questionnaire Hannover (FFbH)	x	x	x	x	x	x	x	x	x
EuroQoL EQ-5D-3L	x	x	x	x	x	x	x	x	x
FACIT – Fatigue Scale	x	x	x	x	x	x	x	x	x
Patient's satisfaction with drug treatment	x	x	x	x	x	x	x	x	x

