7.3.3 POTENTIAL CONFOUNDERS TO BE INCLUDED IN THE PRIMARY ANALYSIS

A number of potential confounders will also be included in the primary analysis and all sensitivity analyses:

- Age at baseline
- Gender
- Duration of disease at baseline
- Indicator of tofacitinib dose
 - 1 if recommended dose of 5mg per day (i.e. TofInterval = BID),
 - 0 if reduced dose of 2.5mg per day (i.e. TofInterval = Daily).
- Poor prognostic factors (PF) indicator (1 if at least one Poor PF is present, 0 otherwise)
- Indicator of dose of MTX or combination partner (1 if increase in dose since last visit, 0 otherwise)
- Indicator of dose of Glucocorticoids (1 if increase in dose since last visit, 0 otherwise)
- Whether patient on 2nd or 3rd line treatment (see below)

A patient is defined as on 2nd line treatment if they were prescribed only csDMARDs prior to enrolling in the study.

A patient is defined as on 3rd line treatment if they were prescribed bDMARDs prior to enrolling in the study.

For a list of the medications considered to be csDMARDs and bDMARDs please see the eCRF.

- Indicator of tolerability issues (1 if treatment termination due to tolerability issues, 0 otherwise).
- Indicator of efficacy issues (1 if treatment termination due to efficacy issues, 0 otherwise).
- Incidence of the following comorbidities documented at the baseline visit (a term will be fitted for each comorbidity with the value 1 if the comorbidity is recorded for a patient or 0 otherwise):
 - Ischemic cardiovascular disease
 - Malignancies
 - Infections
 - Gastro disease
 - Osteoporosis
 - Depression

Any other variables observed to be potential confounders will also be investigated.

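### The SAP's only tolerability term is a flag set by treatment termination, so adverse events before a treatment decision go unadjusted and the satisfaction hazard ratio may be confounded

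*Protocol*

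**What the plan says.** Protocol 7.3 (Table 6) gives the item "RA treatment with Tofacitinib and/or other DMARDs - tolerability" the role of potential confounder and subgroup identifier, with details to follow in the SAP.

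SAP 7.3.3 supplies them. It opens with "A number of potential confounders will also be included in the primary analysis and all sensitivity analyses" and lists, among others, "Indicator of tolerability issues (1 if treatment termination due to tolerability issues, 0 otherwise" and its companion "Indicator of efficacy issues (1 if treatment termination due to efficacy issues, 0 otherwise". SAP 9.2.6 repeats both in every primary and sensitivity row for the number of escalations. SAP 7.3.3 closes with "Any other variables observed to be potential confounders will also be investigated".

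AEs are on the list for visits 2 to 8 (Protocol 7.5.1.2) and for visit 9 (7.5.1.3). The row "Documentation of AE" in the schedule (Protocol 7.5.2) is marked at all nine visits. None of SAP 7.3.1, 7.3.2, 7.3.3 or 9.2.6 contains a term built from these records.

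Satisfaction is one of the six factors in the primary model. The item asks about the arthritis drugs taken since the previous visit. Protocol section 5 says: "Among such criteria, satisfaction with drug treatment is of particular interest".

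**The concern.** A confounder term has to describe the patient before the decision. The SAP flag becomes 1 only through a termination, and termination is one of the three escalation types that make up the primary event (SAP 7.1.1). An AE in a patient who continues treatment leaves it at 0.

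An AE since the last visit can lower the satisfaction score for that same interval. It can also lead the physician to change treatment whatever the patient's satisfaction. The documents make the second route plausible. Protocol 7.5.1.4 provides for withdrawal of treatment after adverse drug reactions, and Protocol 7.6.5 allows only two reasons for a switch, one of which is intolerance. An AE would then be a common cause of the factor and the event. The study could report dissatisfaction as a driver of decisions when part of the driver was a side effect.

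**Working it through.** **What the flag can capture.**

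| Patient in an interval | SAP flag |
|---|---|
| AE, stays on the drug | 0 |
| Stops for intolerance, no new DMARD | 1 |
| Stops for intolerance, starts another DMARD | 0 if termination has its SAP 7.1.1 meaning (no replacement DMARD); 1 if it means a recorded therapy stop, as for tofacitinib in SAP 6.3 and 7.1.2.10 |

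SAP 7.3.3 does not say which meaning applies. It also does not say whether the flag is set only on the row with the event or on all of the patient's rows. The other tolerability data do not fill the gap. The reason for a switch is recorded only when an escalation has occurred (Protocol 7.6.5). The physician's tolerability rating is made at the final visit or at a switch from tofacitinib (Protocol 7.6.19).

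**Size.** The plan states no figure on this point, so there is none to reproduce. The following is an illustration on assumed inputs: 1500 patients (the planned size), 8 quarterly intervals, 60 replicates per scenario.

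- AE in an interval: probability p = 0.10 or 0.20 (assumed).
- Satisfaction = 2.6 − 0.5 × activity − d × AE + noise (SD 0.8), rounded and held to 0–4, with d = 0.5 or 1.0 point (assumed).
- Hazard per interval = 0.05 × exp(0.4 × activity + b × (satisfaction − 2.6)), multiplied by the AE hazard ratio of 1, 2 or 4 if there was an AE (assumed). Event probability = 1 − exp(−hazard).
- True satisfaction HR = exp(b): b = 0 gives 1.00; b = −0.2 gives exp(−0.2) = 0.82.
- Flag: set for an event with an AE with probability 1 − 1/(AE hazard ratio), the share of that hazard due to the AE. Every such event is taken to count as a termination.
- Model: Poisson regression with visit terms, equivalent to an Andersen-Gill Cox model with Breslow ties at common visit times, containing satisfaction and disease activity.

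Satisfaction HR per point, range over the eight scenarios with an AE hazard ratio of 2 or 4:

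| Model | True HR 1.00 | True HR 0.82 |
|---|---|---|
| No tolerability or AE term | 0.73–0.95 | 0.60–0.78 |
| SAP flag on the event row only | 0.98–1.00 | 0.83–0.87 |
| SAP flag as patient-level ever | 0.75–0.96 | 0.63–0.79 |
| Interval-level AE term | 0.99–1.01 | 0.82–0.84 |

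The largest shift is at p = 0.20, d = 1.0 and an AE hazard ratio of 4 (true HR 1.00): 0.725 with no term, 0.989 with the event-row flag, 0.754 with the ever-flag and 0.995 with the AE term. With an AE hazard ratio of 1, the four models agree to within 0.005.

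The event-row result assumes that the flag catches every AE-driven escalation. A separate run used about 8% base escalation per visit and the same AE ranges, and let only 25–50% of AE-driven escalations count as terminations, as the SAP 7.1.1 meaning could imply. At a true HR of 1.00 it gave 0.79–0.97 with no term, 0.83–0.98 with the event-row flag and 0.99–1.01 with an AE term. Across both runs, the model with no term therefore spans 0.73–0.97.

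**The case against.** The strongest reply is that tolerability is not missing. The SAP puts a tolerability indicator in the primary model and in every sensitivity model, so the results with no term are not those of the planned model. This stands. A reader might infer that the satisfaction HR, as planned, is biased away from 1, and the documents do not support that. With the flag on the event row and every intolerance event caught, the shift at a true HR of 1.00 almost disappears. With a true HR of 0.82 the estimate moves slightly towards 1, to 0.83–0.87, although the AE-term model itself reads up to 0.84, so not all of that movement is due to the flag. The near-absence of bias is no endorsement of the flag: on that coding it is 1 only where the event has occurred, so the model conditions on its own outcome.

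A reader might also take it as settled that a switch for intolerance scores 0. It is not, because SAP 6.3 and 7.1.2.10 allow the other reading.

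Three further objections stand in part.

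- AE frequency, the AE effect on escalation and the fall in satisfaction are all assumed.
- The illustration has one disease-activity covariate. The planned model also has the two global assessments, pain and two DAS28 indicators, which may carry part of the link between AEs and satisfaction.
- The plan is not closed to further adjustment. SAP 7.3.3 has its open clause, and Protocol 7.12 foresees sensitivity analyses for confounding. Neither names AEs, defines a variable or commits to including one.

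SAP section 5 calls the model predictive, which would make confounding matter less. The stated objective, however, is to identify what drives treatment decisions (Protocol section 6), so the hazard ratios will be read as influences.

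**Conclusion.** The point holds as a specification gap with a conditional consequence. Protocol Table 6 names tolerability as a confounder. The SAP's version derives from the outcome and cannot represent AEs that arise before a decision, and no model uses the AE records. The satisfaction HR may be confounded as a result.

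This depends on two conditions. AEs must affect escalation other than through satisfaction; if they do not, there is no shift. The flag must also fail to take up that effect, which turns on its unstated coding and on the meaning of termination. Under the assumed inputs and a true HR of 1.00, the planned model could give anything from about 1.00 (event row, all intolerance events caught) to 0.75 (patient-level ever). The documents do not show where in that range the study would fall, and the simulated values are not estimates of its actual bias.

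**What to change.** In SAP 7.3.3 and the model rows of 9.2.6, replace the termination-based tolerability flag with a time-varying indicator, and state it as the operational definition of tolerability in Protocol Table 6:

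- It is 1 if the patient had any AE that the physician judged related to the current RA treatment. Causality is already recorded (Protocol 9.1.2).
- Onset is after the previous visit and strictly before the actual escalation date. In intervals without an escalation, onset is on or before the visit date. The actual date matters because SAP 9.2.2 and 12.1.1 assign escalations to visits by window, so an AE after the switch could otherwise be counted.
- Exclude lack of efficacy and progression or worsening of RA, which Protocol 9.1.3.1 lists as AEs but which reflect disease activity. Exclude abnormal tests that qualify as AEs only because they led to a treatment change.

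Report the satisfaction HR with and without this term, and with an any-AE version as a sensitivity analysis.

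The cost is SAP wording and one derived variable from data already collected. AE under-reporting in routine care would leave some residual confounding.
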